## STUDY SCHEMATIC

### SCHEDULE OF EVENTS

Visit Days → Study Procedure ↓	Screening Period	Clinic Period					Follow-up Period	
	Screening Visit (Day -28 to -2)	Check-in Day -1	1st day of cycle Days 1, 4, 7, 10, 13, 16	2nd day of cycle Days 2, 5, 8, 11, 14, 17	3rd day of cycle Days 3, 6, 9, 12, 15, 18	Discharge Day 19	Follow-up Visit Day 32 (± 2 days)	End of Trial Visit Day 46 (± 3 days)
Informed consent signed	X							
Inclusion/exclusion evaluation	X	X						
Demographics	X							
Medical history	X							
Physical exam	X	X				X		X
HBsAg, HCV & HIV screen	X							
Drug & alcohol screen (a)	X	X					X	
Pregnancy test (b)	X	X					X	X
Weight (W) & height (H) (c)	W, H	W	W			W	W	W
12-lead ECG (d)	X	X	pre: 0 (≤ 15m) pd: 1, 4h (± 15m)			X		
Respiratory rate & oral temp (e)	X	X				X	preNG: 0 (≤ 15m)	X
Clinical chemistry, coagulation, hematology, urinalysis (f)	X	X				X	preEndoPAT (≥1h)	
Hemoglobin A1c	X	X				X	preEndoPAT (≥1h)	
Fasting blood glucose & serum insulin (g)	X	X		pre: 0 (≤15m)		X	preEndoPAT (≥1h)	
Adverse event evaluations	X	X	X	X	X	X	X	X
Prior & concomitant meds	X	X	X	X	X	X	X	X
EndoPAT (h)	X	X			pre: 0 (≤ 1h) pd: 4, 12h (±15m)		preNG: 0 (≤ 1h) pdNG: 45m(±15m)	
Supine/standing BP & pulse supine only (i)	X		pre: 0 (≤ 30m) pd: 1,2,4,8,12h (±10m)		Supine only pre: 0 (≤ 30m) pd: 1,2,8h (±10m)	24h (± 15m)	Supine only preNG: 0 (≤ 30m) pdNG: 2h (+30m)	

Visit Days → Study Procedure ↓	Screening Period	Clinic Period					Follow-up Period	
	Screening Visit (Day -28 to -2)	Check-in Day -1	1 st day of cycle Days 1, 4, 7, 10, 13, 16	2 nd day of cycle Days 2, 5, 8, 11, 14, 17	3 rd day of cycle Days 3, 6, 9, 12, 15, 18	Discharge Day 19	Follow-up Visit Day 32 (± 2 days)	End of Trial Visit Day 46 (± 3 days)
[REDACTED]								
Platelet function (k)			pre: 0 (≤ 15m) pd: 4h (± 15m)					
Pharmacokinetic samples (l)			pre: 0 (≤ 15m) pd: 1,3,6,12h (± 5m)	pre: 0 (≤15m)		24h (± 15m)	preEndoPAT (≥1h)	X
[REDACTED]			[REDACTED]			[REDACTED]	[REDACTED]	[REDACTED]
[REDACTED]			[REDACTED]			[REDACTED]	[REDACTED]	[REDACTED]
Study drug administration (o)			X	X	X			
Ambulatory BP monitoring				Start: pre 0(≤30m) End: pd12h(+30m)				
Confined to clinic		X	X	X	X			
Discharge from clinic						X		
Nitroglycerin administration (p)							X	
Study completion								X

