### **3.7.3 Safety Assessments**

#### **3.7.3.1 Physical Examination**

A complete physical examination will be performed according to the Schedule of Events. The physical examination of each patient should include examination and assessment of the following:

General appearance	Lymph nodes	Musculoskeletal system
Cardiovascular system	Neurologic status	Nervous system
Respiratory system	Head, eyes, ears, nose, and throat	Skin
Abdomen/liver/spleen	Neck	Mental status

Breast, genitourinary, and rectal examinations are optional and may be performed at the discretion of the Investigator. Any new, clinically significant abnormal findings from the physical examination will be reported as an AE.

Height will only be recorded at the Screening Visit; weight will be recorded according to the Schedule of Events.

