### **3.7.3.7 Recording Adverse Events**

Adverse events will be collected and recorded from the time the patient signs the ICF at the Screening Visit through the End of Trial Visit. All AEs, regardless of the assumption of a causal relationship with study procedures or study medication, must be recorded in the patient's source documentation and subsequently on the appropriate AE page of the patient's eCRF. This record includes AEs the patient reports spontaneously, those observed by the Investigator, and those elicited by the Investigator in response to open-ended questions during the study, such as "Have you had any health problems since your last visit?"

For every AE, the Investigator must

- Provide an assessment of the severity, causal relationship to the study medication, and seriousness of the event
- Document all actions taken with regard to the study medication (ie, no action taken, treatment temporarily interrupted, or treatment discontinued)
- Detail any other treatment measures taken for the AE, including concomitant medications and/or procedures

Pretreatment AEs will be collected from the time the patient signs the ICF until the patient receives study drug. Pretreatment AEs will be captured in the patient's source documentation but will only be entered for patients who receive study drug on the AE page of the patient's eCRF.

Laboratory abnormalities and changes in vital signs, physical examination findings, and 12-lead ECG parameters should be considered AEs and reported on the AE page of the patient's eCRF if the Investigator considers them clinically significant and/or they necessitate intervention.

Any medical condition that is present when a patient is screened and does not worsen in severity and/or frequency should be reported as Medical History and not as an AE. However, if the condition does deteriorate in severity and/or frequency at any time during the study, it should be reported as an AE.

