### **3.8.2.5 Discharge (Day 19)**

- Weight
- Supine-to-standing (orthostatic) pulse and BP at 24 hours ( $\pm 15$  minutes) postdose
- Physical examination
- 12-lead ECG
- Respiratory rate and oral temperature
- Collection of blood and urine samples for clinical laboratory test, including:
  - PK blood sample at 24 hours ( $\pm 15$  minutes) postdose
  - 
  - Clinical chemistry
  - Hematology (CBC)
  - Coagulation
  - Urinalysis
  - Hemoglobin A1c
  - Fasting blood glucose
  - Serum insulin
- AE evaluation
- Concomitant medications
- Discharge from the clinic

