### 3.8.3 Follow-up Period (Day 20 to Day 46 $\pm$ 3)

#### 3.8.3.1 Follow-up Visit (Day 32 $\pm$ 2)

- Collection of blood samples for the following assessments  $\geq$  1 hour before predose EndoPAT assessment:
  - PK
  - [REDACTED]
  - Clinical chemistry
  - Hematology (CBC)
  - Coagulation
  - Hemoglobin A1c
  - Fasting blood glucose
  - Serum insulin
- Collection of urine samples for the following assessments predose ( $\geq$  1 hour)
  - Urine pregnancy test for all females (must be confirmed negative before nitroglycerin dose)
  - Urinalysis
  - Drug screen
- Weight
- Alcohol breathalyzer
- EndoPAT assessment predose ( $>$  1 hour after blood draws and  $\leq$  1 hour before nitroglycerin dose)
- Supine BP and pulse predose ( $\leq$  30 minutes)
- Respiratory rate and oral temperature predose ( $\leq$  15 minutes)
- Sublingual nitroglycerin administration according to label
- EndoPAT assessment postdose (45 minutes [ $\pm$  15 minutes] after nitroglycerin dose)
- Supine BP and pulse 2 hours (+ 30 minutes) postdose
- AE evaluation
- Concomitant medications

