7.9.1 Adverse Events

All adverse events (AEs) will be coded using the Medical Dictionary for Regulatory Activities (MedDRA) Version 19.1 and will be classified by MedDRA system organ class (SOC), and preferred term (PT).

Treatment-emergent adverse events (TEAEs) are those AEs that started or worsened in severity after the administration of study drug. If it is not possible to determine when the event started due to incomplete start dates/times, it will be assumed to be treatment emergent.

TEAEs will be assigned to the cycle in which they originated. That is, TEAEs that started on or after the first dose of study drug in a cycle but before dosing in the next cycle will be assigned to the treatment received in that cycle. Adverse events that occurred after the Nitroglycerin administration during the follow-up period will be summarized separately.

The number and percentage of patients who experience at least one TEAE as well as those who experience each specific SOC and PT will be presented by cycle group as well as overall using the Safety Population. Subgroup analyses of TEAEs will also be presented by race (blacks vs. non-blacks). Summaries of study drug related TEAEs will also be presented by cycle group.

Prevalent TEAEs in a cycle are defined as TEAEs that either started in or continued into a cycle, and will be presented by SOC and PT for each cycle group using the Safety Population.

For presentation of AE incidence, AEs will be sorted alphabetically by SOC, and within each SOC, by decreasing incidence of PT in the overall group.

In addition, TEAEs, severe TEAEs, drug-related AEs (those that are determined by the Investigator to be related to study drug), serious AEs, AEs that resulted in study discontinuation, and AEs that resulted in death (if any) will be presented in separate listings.

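### After first dosing, the scheduled safety labs and examinations fall only after the last dose, so by-cycle TEAE incidence is biased upward at the last dose received

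*SAP*

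**What the plan says.** **What becomes an AE.** Protocol 3.7.3.7 says that "Laboratory abnormalities and changes in vital signs, physical examination findings, and 12-lead ECG parameters should be considered AEs" when the Investigator judges them clinically significant or they need intervention. Protocol 3.7.3.1 adds: "Any new, clinically significant abnormal findings from the physical examination will be reported as an AE".

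**When the tests are done.** In the Schedule of Events, chemistry, hematology, coagulation, urinalysis and HbA1c are taken at Screening, Check-in (Day -1), Discharge (Day 19) and the Follow-up Visit (Day 32, before nitroglycerin). Physical examination is at Screening, Check-in, Day 19 and Day 46. Temperature and respiratory rate follow the same pattern as the examination, plus Day 32 before nitroglycerin. The task lists for the three cycle days (Protocol 3.8.2.2 to 3.8.2.4) include none of these. They do include daily AE evaluation and, in every cycle, ECG, cuff BP and pulse, and fasting glucose and insulin.

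**How events are assigned.** SAP 7.9.1 assigns to a cycle's treatment the "TEAEs that started on or after the first dose of study drug in a cycle but before dosing in the next cycle". The only exception after the last cycle is that "Adverse events that occurred after the Nitroglycerin administration during the follow-up period will be summarized separately". TEAE incidence "will be presented by cycle group as well as overall using the Safety Population". Patients who stop early complete the Discharge assessments after their own final dose (Protocol 3.6).

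**The concern.** Safety and tolerability across escalating doses is the first-listed objective, and the by-cycle TEAE table is where a reader will look for a dose trend. The placebo cycle is meant to serve as the patients' own control (Protocol 3.2, SAP 3.2). For findings that only a laboratory panel or an examination would reveal, however, the placebo and intermediate-dose columns have no scheduled chance to show an event, and the last-dose column does. A difference could then come from when the tests were done and not from the dose. For completers the column affected is 50 mg, which Protocol 3.5.2 says exceeds the maximum tolerated dose in healthy volunteers. That is the column where an artificial rise would be most easily misread.

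**Working it through.** The documents give no AE rate, power or effect size on this point, and the sample size of 12 is stated to be non-statistical, so there is no plan figure to reproduce. The check has two parts.

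**1. Scheduled assessments inside each SAP 7.9.1 window (patient completing all cycles).** The days come from the Schedule of Events. The last window is taken to run from Day 16 to nitroglycerin on Day 32.

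| Window | Lab panels and HbA1c | Physical examination | Temperature, respiratory rate | Fasting glucose, insulin |
|---|---|---|---|---|
| Placebo, 10, 20, 30, 40 mg (each) | 0 | 0 | 0 | 1 |
| 50 mg | 2 (Days 19, 32) | 1 (Day 19) | 2 (Days 19, 32) | 3 (Days 17, 19, 32) |

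The Day 46 examination follows nitroglycerin and is reported separately, so it does not enter the 50 mg column. The last window is also longer: 32 − 16 = 16 days against 3, or 16/3 = 5.3 times as long. With the ± 2 day visit window this is 14/3 = 4.7 to 18/3 = 6.0. That is a related gap. Closing the window after Discharge would still leave the Day 19 findings in the last-dose column.

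**2. Illustrative size.** Let q be the probability that a patient has a new, clinically significant and otherwise silent finding at these post-dose assessments, unrelated to dose. The values of q are assumptions. N = 12, all completing, patients independent.

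- Weight of one patient: 1/12 = 8.3 percentage points.
- Expected patients in the last-dose column from this source: 12q.
- Chance of at least one: 1 − (1 − q)^12.

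| q | 12q | Chance of at least one | Expected in every other column |
|---|---|---|---|
| 5% | 0.6 | 1 − 0.95^12 = 46% | 0 |
| 10% | 1.2 | 1 − 0.90^12 = 72% | 0 |
| 15% | 1.8 | 1 − 0.85^12 = 86% | 0 |

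These figures count patients with such a finding. In the any-TEAE row the addition is smaller, because SAP 9.2 counts each patient once per cycle. Let b be the probability of another TEAE in the last cycle, assumed to be 20% and independent of the finding. The expected addition is 12(1 − b)q, and the chance of at least one added patient is 1 − (1 − 0.8q)^12.

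| q | 12 × 0.8 × q | Chance of at least one | Any-TEAE incidence, 1 − 0.8(1 − q), against 20% elsewhere |
|---|---|---|---|
| 5% | 0.48 | 39% | 24% |
| 10% | 0.96 | 63% | 28% |
| 15% | 1.44 | 78% | 32% |

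**The case against.** **Onset is not detection.** The SAP assigns by start, not by the date of a test. Patients are confined, with AE evaluation every day, so a symptomatic or visible finding can be recorded in an earlier cycle or dated to its true onset. Unscheduled assessments are also foreseen (SAP 9.1). This stands, and it limits the point to otherwise silent findings. For those, nothing scheduled between Day -1 and Day 19 could place the onset earlier, and neither document gives a rule for dating an abnormality found by a test. The prevalent-TEAE table does not help, because it also depends on the start date.

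**The affected set is narrow.** Only clinically significant findings, or those needing intervention, become AEs. ECG, cuff BP, pulse, fasting glucose and insulin are checked in every cycle and are outside this point. That stands too.

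**Nothing inferential rests on the table.** The safety analyses are descriptive (SAP 6.1, 6.6), all TEAEs are listed, and 12 patients can be inspected one by one. This lowers the stakes, but the summary table still carries the tilt without saying so. SAP 7.9.2 presents most laboratory values overall by timepoint and gives by-cycle changes only for glucose and insulin. SAP 7.9.1 has no matching rule for the AEs that arise from the same panels.

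**Stronger readings that the documents do not support.** A reader might infer that such AEs can arise only at Discharge. They cannot be so confined: labs recur on Day 32, the examination recurs on Day 46, and unscheduled tests are possible. A reader might also infer that the excess always falls at 50 mg. For early stoppers it falls at the stopping dose. Finally, a reader might infer that 50 mg incidence will in fact be raised. No rate is given, and the effect is zero if no such finding occurs.

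**Conclusion.** The point holds for otherwise silent findings first picked up by the scheduled post-dose laboratory panels, HbA1c, examination, temperature or respiratory rate. The direction of the bias follows from the schedule and the assignment rule alone: upward at the last dose received, with no scheduled counterpart in the placebo or earlier cycles. The size cannot be known from the documents and may be zero. The figures of 0.6, 1.2 and 1.8 patients rest on assumed rates of 5%, 10% and 15%, no dose effect and all 12 patients completing. The any-TEAE row would gain fewer, by an amount that depends on an assumed background rate. With one patient worth 8.3 points, even one or two such findings could look like a step up at the top dose. The analysis is descriptive and the listings will be complete, so this is an inexpensive correction to the display. It does not threaten the trial.

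**What to change.** In SAP 7.9.1, split the last-dose display by onset date:

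- **(a)** TEAEs with onset from the first dose of the last cycle up to the start of the Discharge assessments. For a completer this is about 3 days, in line with the other cycles.
- **(b)** TEAEs with onset at or after the start of the Discharge assessments and before nitroglycerin, shown beside (a) by last dose received.

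Base the comparison across cycles on (a). Keep every event in the overall column and in the listings, and keep the separate post-nitroglycerin summary. Add a footnote saying that the tests in question are not scheduled during the cycles.

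A split by date is better than one by how the event was found. Detection source is not among the items that Protocol 3.7.3.7 requires for each AE, so it would have to be inferred, and taking events away from 50 mg on that basis could obscure a real late signal.

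The cost is SAP wording and one extra column, with no new assessments. The downside is small: a true late effect of the last dose would appear in (b) and not in (a). So would a Day 19 ECG or cuff BP finding, although the corresponding predose finding on the first day of the next cycle counts toward the earlier cycle. Showing (b) next to (a) keeps both visible.

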### **3.3 STUDY DURATION**

Patients will receive once-daily study drug for 18 days: placebo for 3 days and escalating doses of IW-1973 for 15 days. Patients will be in clinic for 20 days, from Check in on Day -1 to Discharge on Day 19. Total patient participation will be 45 to 77 days including Screening, Clinic, and Follow-up Periods.

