3. STUDY DESIGN

3.1 GENERAL DESCRIPTION

This open-label, single-center trial will enroll 12 patients (at least 4 men and 4 women) to receive once-daily study drug for 6, sequential, 3-day dosing cycles (18 total days) starting with placebo (baseline) for 3 days and then progressing to 5 escalating dose levels of IW-1973 (10, 20, 30, 40, and 50 mg) for 3 days each. Patients will be in clinic for 20 days, from Check-in on Day -1 to Discharge on Day 19. Total patient participation will be 45 to 77 days.

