6. STATISTICAL METHODS

6.1 GENERAL METHODOLOGY

Descriptive statistics (number of patients, mean, standard deviation, median, minimum and maximum) will be calculated for continuous variables. For summaries of continuous PK parameters, the geometric mean and the coefficient of variation (CV) will also be presented. For summaries of continuous PD parameters, the CV, 95% confidence intervals (CI), as well as the 25th and 75th percentiles will be presented. For categorical variables, frequencies and percentages for each category will be presented. Percentages will be based on the total number of patients with non-missing values. If there are missing values, the number missing will be presented, but without a percentage.

Inferential statistics, if calculated, will only be used for descriptive purposes.

All statistical analyses will be performed using SAS Version 9.1 or later [1]. Additional analyses using alternative software may be performed as part of the pharmacokinetic analysis.

Summary data will be presented by cycle group:

- Placebo
- IW-1973 10 mg
- IW-1973 20 mg
- IW-1973 30 mg
- IW-1973 40 mg
- IW-1973 50 mg

Definition of Baseline:

The following definitions of baseline will be used to calculate change from baseline parameters, unless specified otherwise-

- Study baseline is defined as the last non-missing assessment before first administration of study drug, that is, the Day -1 assessment.

- Time-matched baseline for each day/timepoint in the IW-1973 cycles is defined as the corresponding assessment during the placebo cycle.
- Cycle baseline is defined as the assessment taken prior to drug administration at the beginning of each cycle.
- Trough baseline is defined as the last assessment prior to initiation of IW-1973 administration, that is, the Study Day 4 predose assessment.

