8. CHANGES IN THE CONDUCT OF THE STUDY OR PLANNED ANALYSES

The following analyses will be performed in addition to those described in the study protocol.

- Change from cycle baseline (defined as the assessment taken prior to drug administration at the beginning of each cycle) will be presented for cuff BP assessments (supine systolic BP, diastolic BP, and pulse), RHI assessments, and platelet function assessments.
- Change from trough baseline (defined as the last assessment prior to initiation of IW-1973 administration, that is, the Study Day 4 predose assessment) will be presented for trough supine systolic BP, diastolic BP, and pulse.
- Subgroup analyses by race (blacks vs. non-blacks) will be performed for daytime ABPM assessments and adverse events.
- Prevalent TEAEs in a cycle, defined as TEAEs that either started in or continued into a cycle, will be presented by SOC and PT for each cycle group using the Safety Population.
- Change from time-matched baseline (placebo cycle) will be presented for blood glucose, serum insulin and QTc-F for each scheduled postdose assessment.
- Change from study baseline in ECG assessments will be summarized only for the predose assessments in each cycle.

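### The prevalent-TEAE table in SAP 7.9.1 and Section 8 is not comparable between placebo and IW-1973 columns, because only the active columns can contain carried-in events

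*SAP*

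**What the plan says.** SAP 7.9.1 defines treatment emergence this way: "Treatment-emergent adverse events (TEAEs) are those AEs that started or worsened in severity after the administration of study drug". Its main adverse event table works by origin: "TEAEs will be assigned to the cycle in which they originated". It then adds a second, prevalence-type table: "Prevalent TEAEs in a cycle are defined as TEAEs that either started in or continued into a cycle". SAP Section 8 lists this among the analyses added to the protocol and says that these events "will be presented by SOC and PT for each cycle group using the Safety Population". The cycle groups in SAP 6.1 include placebo.

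Placebo falls under study drug. Protocol 3.3 says: "Patients will receive once-daily study drug for 18 days: placebo for 3 days and escalating doses of IW-1973 for 15 days". The order is fixed; SAP 3.1 describes treatment "for 6, sequential, 3-day dosing cycles (18 total days) starting with placebo (baseline) for 3 days". Events before the first dose form a separate class under Protocol 3.7.3.7: "Pretreatment AEs will be collected from the time the patient signs the ICF until the patient receives study drug".

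The SAP text does not divide the prevalent table into its two components and gives no caution about reading across its columns.

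**The concern.** The two halves of the definition do not apply equally to all columns. An event already present at the first placebo dose is a pretreatment event unless it worsens, so nothing can continue into the placebo cycle as a TEAE. The 10 mg column can receive events from placebo. The 20 to 50 mg columns can receive events from placebo and from every lower dose. A mild, persistent event that began on placebo is tabulated under 10 mg and under each later dose while it lasts.

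Safety and tolerability of escalating doses is the first objective, and the placebo cycle is each patient's only control. A table that sets placebo beside the five doses will be read as that comparison. The carry-in works in one direction only: it adds to the active columns and never to placebo.

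**Working it through.** **Inputs from the documents.** Six cycles of 3 days, placebo first (SAP 3.1); 12 patients (SAP 4); the TEAE and prevalence definitions (SAP 7.9.1). The first dose comes after Day -1: SAP 6.1 defines study baseline as the "last non-missing assessment before first administration of study drug, that is, the Day -1 assessment". The documents give no adverse event rate or duration, so there is no figure of the plan's to reproduce.

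**Assumptions.** No drug effect; a constant onset rate L per patient-day in all cycles; exponential duration with mean d days; all patients complete; a 3-day window for every cycle, including 50 mg. Let p be the percentage of patients with a new event per cycle.

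**Formulas.**
- L = -ln(1 - p)/3. For p = 20%, L = 0.2231/3 = 0.0744 per day.
- Expected carried-in events in cycle k: C(k) = L × d × (1 - exp(-3(k - 1)/d)). For placebo, k = 1 and C = 0 exactly.
- Patients with a prevalent event in cycle k: 1 - exp(-(3L + C(k))).

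**Example, p = 20%, d = 3, 50 mg (k = 6).** C = 0.0744 × 3 × (1 - exp(-5)) = 0.2216. Prevalence = 1 - exp(-(0.2231 + 0.2216)) = 35.9%. The carried-in share of events is 0.2216/0.4448 = 50%.

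**Results for p = 20% (percentage of patients).**

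| Mean duration | Placebo | 10 mg | 20 mg | 30 mg | 40 mg | 50 mg | Carried-in share of events at 50 mg |
|---|---|---|---|---|---|---|---|
| 0.25 day | 20.0 | 21.5 | 21.5 | 21.5 | 21.5 | 21.5 | 8% |
| 1 day | 20.0 | 25.5 | 25.7 | 25.7 | 25.7 | 25.7 | 25% |
| 3 days | 20.0 | 30.5 | 34.0 | 35.3 | 35.7 | 35.9 | 50% |
| 6 days | 20.0 | 32.9 | 39.7 | 43.4 | 45.6 | 46.9 | 65% |

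In patients, the 3-day row is 12 × 0.200 = 2.4 on placebo against 12 × 0.359 = 4.3 at 50 mg, a difference of about 2 of 12.

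**Other onset rates.** At p = 10%, 50 mg reaches 13%, 19% and 26% for 1, 3 and 6 days. At p = 25% and d = 3, the columns run 25.0, 37.5, 41.5, 42.9, 43.5, 43.6%. A simulation of 200,000 patients at p = 25% (d = 1 and d = 3) agreed with the formula within 0.2 points. New-onset incidence stayed flat at 25% in all six cycles.

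**Sensitivity to constant onset.** With p = 25% and onsets doubled in the placebo cycle, d = 1 gives 43.7% on placebo against 37.5% at 10 mg. Carry-in still adds to the 10 mg figure, but the observed pattern falls.

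**Sensitivity to the 50 mg window.** The origin rule closes a cycle at dosing in the next one, and 50 mg has no next cycle. If its window ran from Day 16 to the nitroglycerin visit on Day 32 (assumed 16 days), null new-onset at p = 20% would be 1 - exp(-16 × 0.0744) = 70%, against 20% on placebo. The carried-in share would fall to 6%, 16% and 26% for 1, 3 and 6 days.

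**The case against.** The best defence is that the table does what its definition says. A prevalence table shows the burden present at each dose, including continuing events. The origin-based table stands beside it, and the excess of one over the other points to carry-in. SAP 6.6 calls the safety analyses qualitative, SAP 6.1 limits any inference to description, and the stopping criteria in Protocol 3.6 do not use this table. SAP Section 1 places table specifications in a separate document, so a split or footnote may already exist there.

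Much of this stands, and it limits the consequence. It does not make the columns comparable. Nor do the two tables recover the split exactly: SAP 9.2 counts a patient once per SOC or PT within a cycle, so the difference shows only patients with a carried-in event and no new one.

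Three stronger readings are tempting and not supported:
- *Prevalence must rise from placebo to active doses.* This is an expectation under constant onset. It can fail if onsets cluster in the placebo cycle, and the rise is small if events resolve within hours.
- *Between 25% and 65% of prevalent events at 50 mg are carried in.* That range needs mean durations of 1 to 6 days and a 3-day window at 50 mg. The documents set neither.
- *Pretreatment events could fill the gap in the placebo column.* They are not TEAEs. Protocol 3.7.3.7 records unworsened conditions present at screening as medical history, and Protocol 3.1 lets screening last as little as 1 day. At p = 20% and d = 3, one day of accrual gives 1 - exp(-(0.2231 + 0.0744 × 3 × (1 - exp(-1/3)))) = 25%, against the 36% needed to match later cycles.

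**Conclusion.** The point holds as a matter of definition. The placebo column can contain only new or newly worsened TEAEs, while every IW-1973 column also contains carried-in ones, so total prevalence should not be compared between them. Events with an undeterminable start date are presumed treatment-emergent, but that exception does not give placebo carry-in comparable to later cycles.

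The size is uncertain. Under no drug effect, constant 20% onset and 3-day windows, the excess at 50 mg over placebo runs from about 1.5 percentage points (0.25-day mean duration) to 27 points (6-day).

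A reader might infer that the trial's tolerability assessment is compromised, or that the origin-based table is already a clean comparator. The documents support neither. The prevalent table is a supplementary, descriptive display. The origin-based table is free of carry-in, but its 50 mg window has no stated end. This is worth correcting in the SAP, at modest priority.

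**What to change.** In SAP 7.9.1 and Section 8:
- Keep the prevalent table, but split each cycle column into (a) started in this cycle, (b) carried in from the placebo cycle and (c) carried in from a lower IW-1973 dose.
- Add a footnote that the placebo column cannot contain carried-in TEAEs, so total prevalence is not comparable across columns.
- State that placebo-to-dose comparison rests on new onsets over equal 3-day windows. Give the 50 mg cycle an explicit end for this purpose, and show later onsets separately as follow-up.
- Do not add pretreatment events to the placebo column.

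The cost is SAP wording and reprogramming of the affected adverse event tables, with no new data. The drawback is a longer, sparse table: with 12 patients, most SOC and PT cells will be 0 or 1. If the separate table specifications already provide the split, only the footnote and the window rule need adding.
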